#### 12.8.6 Physical examination

Output name	Display*	Title (Description)	Analysis set(s)**	Key deliverable	Mock layout	SAP section
PHYPS	L	Subject listing of physical examination data by visit (Baseline, Week 6 and Week 10)	SAF		Layout L14	10.12.5

\* S=Summary table, L= Listing, F=Figure, \*\* SCR=Screened set, FAS=Full Analysis set, SAF=Safety set, RAN=Randomized set, PPS=Per protocol set, PKS=Pharmacokinetic analysis set

## 13 APPENDICES

### APPENDIX A - TABLE, FIGURE AND LISTING LAYOUTS

#### 13.1 TABLE LAYOUTS

##### 13.1.1 Layout T1

Study MMED007 - Deliverables: <Deliverables>  
 Table <Number of table>  
 <Title>  
 Analysis set: <analysis set>

	MM-120 N=xx	Placebo N=xx	All N=xx N (%)
Screened Set (SCR) Subjects Included			xx (100%)
Randomized Set (RAN) *			
Subjects Included	xx	xx	xx (yy.y)
Subjects Excluded			xx (yy.y)
Safety Set (SAF) **			
Subjects Included	xx	xx	xx (yy.y)
Subjects Excluded	xx	xx	xx (yy.y)
Full Analysis Set (FAS) **			
Subjects Included	xx	xx	xx (yy.y)
Subjects Excluded	xx	xx	xx (yy.y)
Per Protocol Set (PPS) ***			
Subjects Included	xx	xx	xx (yy.y)
Subjects Excluded	xx	xx	xx (yy.y)
Pharmacokinetic Analysis Set (PKS) ^			
Subjects Included	xx		xx (yy.y)
Subjects Excluded			xx (yy.y)

\*Percentages are calculated on the SCR

\*\*Percentages are performed on the RAN

\*\*\*Percentages are performed on the FAS

^ Percentages are performed on the SAF

Program: [program\\_name.sas](#), Produced on yyyy-mm-dd hh:mm (CET),

[Snapshot date: yyyy-mm-dd, Draft/](#)[final](#)

Page x of x

##### 13.1.2 Layout T2

Study MMED007 - Deliverables: <Deliverables>  
 Table <Number of table>  
 <Title>  
 Analysis set: <analysis set>

	MM-120 N=xx	Placebo N=xx	All N=xx N (%)
Subjects screened	xx	xx	xx (100%)
Screen failures			xx (yy.y)
Subjects randomized	xx	xx	xx (yy.y)
Subjects treated	xx	xx	xx (yy.y)
Subjects who completed the study	xx	xx	xx (yy.y)
Subjects who prematurely discontinued the study, reasons:			
Lost to follow-up	xx	xx	xx (yy.y)
Death	xx	xx	xx (yy.y)
COVID-19 related	xx	xx	xx (yy.y)
Other	xx	xx	xx (yy.y)

Program: [program\\_name.sas](#), Produced on yyyy-mm-dd hh:mm (CET),

[Snapshot date: yyyy-mm-dd, Draft/](#)[final](#)

Page x of x

##### 13.1.3 Layout T3

Study MMED007 - Deliverables: <Deliverables>

Table <Number of table>

<Title>

Analysis set: <analysis set>

	MM-120 N=xx N (%)	Placebo N=xx N (%)	All N=xx N (%)
<categorical parameter> [n (%)]			
<category 1>	xx (yy.y)	xx (yy.y)	xx (yy.y)
.			
<category n>	xx (yy.y)	xx (yy.y)	xx (yy.y)
<continuous parameter> (unit)			
n	xx	xx	xx
Mean	xx.x	xx.x	xx.x
Standard deviation	xx.x	xx.x	xx.x
Median	xx.x	xx.x	xx.x
Q1, Q3	xx.x, xx.x	xx.x, xx.x	xx.x, xx.x
Min, Max	xx.x, xx.x	xx.x, xx.x	xx.x, xx.x

Program: [program\\_name.sas](#), Produced on yyyy-mm-dd hh:mm (CET),

Snapshot date: yyyy-mm-dd, Draft/final

Page x of x

Note for programmer:

- For table "SDEM" use: sex at birth (male | female) at screening, profession, highest education level (less than primary, primary, secondary, tertiary [bachelor, master, doctoral degree]) and country as categorical; age at screening as continuous.
- For table "SBDC" use: Baseline values for the Adult Attention Deficit Investigator Symptom Rating Scale (AISRS), Clinical Global Impression - Severity of Illness Scale (CGI-S), Adult ADHD Self-Report Scale (ASRS) and Connors' adult ADHD rating scale self-report long form (CAARS-L-SR) as continuous.  refer to scores on baseline 'Patient Reported Outcomes' eCRF page to be summarized in the table. In the table scores  should be reported as: A=Inattention/Memory Problems; B=Hyperactivity/Restlessness; C=Impulsivity/Emotional Lability; D=Problems with Self-Concept; E=DSM-IV Inattentive Symptoms; F=DSM-IV Hyperactive-Impulsive Symptoms; G=DSM-IV ADHD Symptoms Total; H=ADHD Index.
- For table "SCPT" use: 'Stop Signal Task', 'Discounting Task', 'Psychomotor Vigilance Task', 'Time Production Task' and 'Time Reproduction Task' categories at Baseline and Week 6; the number (%) of completers and non-completers of the test by the answer 'Yes|No' to the question Cognitive performance tests performed?.

### 13.1.4 Layout T4

Study MMED007 - Deliverables: <Deliverables>

Table <Number of table>

<Title>

Analysis set: <analysis set>

<Medical history/Concomitant diseases>

System Organ Class / Preferred Term	MM-120 N=xx N (%)	Placebo N=xx N (%)	All N=xx N (%)
ALL SYSTEM ORGAN CLASSES			
Total number of subjects with at least one <medical and psychiatric events   AE>	xx (yy.y)	xx (yy.y)	xx (yy.y)
System Organ Class 1 <preferred term1> <preferred term2>	xx (yy.y) xx (yy.y) xx (yy.y)	xx (yy.y) xx (yy.y) xx (yy.y)	xx (yy.y) xx (yy.y) xx (yy.y)
System Organ Class n <preferred term1> <preferred term2>	xx (yy.y) xx (yy.y) xx (yy.y)	xx (yy.y) xx (yy.y) xx (yy.y)	xx (yy.y) xx (yy.y) xx (yy.y)

System Organ Class and Preferred terms are based on MedDRA 25.1 dictionary.

Program: [program\\_name.sas](#), Produced on yyyy-mm-dd hh:mm (CET),

Snapshot date: yyyy-mm-dd, Draft/final

Page x of x

Note for programmer: display medical history and concomitant diseases in separate pages.

Please use 'System Organ Class and' only in tables by SOC and PT and not in those only by PT.

Please add footnote 'Treatment-emergent adverse events are events with onset date/time between the study treatment start date and the study treatment end date, limits included.' In the tables with treatment-emergent AEs.

Please add footnote 'A Serious Adverse Reaction (SAR) is a serious adverse event that is determined to be related to the study treatment' to the table with Summary of serious adverse reaction (SAR) by system organ class (SOC) and individual preferred term (PT).

### 13.1.5 Layout T5

Study MMED007 - Deliverables: <Deliverables>

Table <Number of table>

<Title>

Analysis set: <analysis set>

Anatomical Therapeutic Chemical Class / Preferred Term	MM-120 N=xx N (%)	Placebo N=xx N (%)	All N=xx N (%)
ALL THERAPEUTIC CLASSES			
Total number of subjects with at least one medication	xx (yy.y)	xx (yy.y)	xx (yy.y)
Total number of medication	xx	xx	xx
ATC class 1			
Total number of subjects with at least one medication	xx (yy.y)	xx (yy.y)	xx (yy.y)
Total number of medication	xx	xx	xx
<preferred term1>	xx (yy.y)	xx (yy.y)	xx (yy.y)
<preferred term2>	xx (yy.y)	xx (yy.y)	xx (yy.y)
ATC class n			
Total number of subjects with at least one medication	xx (yy.y)	xx (yy.y)	xx (yy.y)
Total number of medication	xx	xx	xx
<preferred term1>	xx (yy.y)	xx (yy.y)	xx (yy.y)
<preferred term2>	xx (yy.y)	xx (yy.y)	xx (yy.y)

ATC= Anatomical Therapeutic Chemical Class

Program: [program\\_name.sas](#), Produced on yyyy-mm-dd hh:mm (CET),

Snapshot date: yyyy-mm-dd, Draft/final

Page x of x

### 13.1.6 Layout T6

Study MMED007 - Deliverables: <Deliverables>

Table <Number of table>

<Title>

Analysis set: <analysis set>

	MM-120 N=xx	Placebo N=xx
Exposure (days)	xx	xx
n	xx.x	xx.x
Mean	xx.x	xx.x
Standard Deviation	xx.x	xx.x
Standard Error	xx.x	xx.x
Median	xx.x	xx.x
Q1 , Q3	xx.x, xx.x	xx.x, xx.x
Min , Max	xx.x, xx.x	xx.x, xx.x

Program: [program\\_name.sas](#), Produced on yyyy-mm-dd hh:mm (CET),

Snapshot date: yyyy-mm-dd, Draft/final

Page x of x

### 13.1.7 Layout T7

Study MMED007 - Deliverables: <Deliverables>

Table <Number of table>

<Title>

Analysis set: <analysis set>

	MM-120 N=xx N (%)	Placebo N=xx N (%)
Subjects who did not complete the trial	xx (yy.y)	xx (yy.y)
Reason for premature trial discontinuation		
Lost to follow-up	xx (yy.y)	xx (yy.y)
Death	xx (yy.y)	xx (yy.y)
COVID-19 related	xx (yy.y)	xx (yy.y)
Other	xx (yy.y)	xx (yy.y)
xxx	xx (yy.y)	xx (yy.y)

Program: [program\\_name.sas](#), Produced on yyyy-mm-dd hh:mm (CET),

Snapshot date: yyyy-mm-dd, Draft/final

Page x of x

### 13.1.8 Layout T8

Study MMED007 - Deliverables: <Deliverables>

Table <Number of table>

<Title>

Analysis set: <analysis set>

Visit

	MM-120	Placebo	All
--	--------	---------	-----

Preferred Term	N=xx N (%)	N=xx N (%)	N=xx N (%)
ALL SYSTEM ORGAN CLASSES			
Total number of subjects with at least one AE	xx (yy.y)	xx (yy.y)	xx (yy.y)
<preferred term1>	xx (yy.y)	xx (yy.y)	xx (yy.y)
<preferred term2>	xx (yy.y)	xx (yy.y)	xx (yy.y)

Preferred terms are based on MedDRA 25.1 dictionary.

Program: [program\\_name.sas](#), Produced on yyyy-mm-dd hh:mm (CET),  
 Snapshot date: yyyy-mm-dd, Draft/final

Page x of x

### 13.1.9 Layout T9

Study MMED007 - Deliverables: <Deliverables>

Table <Number of table>

<Title>

Analysis set: <analysis set>

System organ class Preferred term	MM-120 N=xx N (%)	Placebo N=xx N (%)	All N=xx N (%)
All deaths	xx (yy.y)	xx (yy.y)	xx (yy.y)
System organ class 1	xx (yy.y)	xx (yy.y)	xx (yy.y)
<preferred term1>	xx (yy.y)	xx (yy.y)	xx (yy.y)
<preferred term2>	xx (yy.y)	xx (yy.y)	xx (yy.y)
System organ class n	xx (yy.y)	xx (yy.y)	xx (yy.y)
<preferred term1>	xx (yy.y)	xx (yy.y)	xx (yy.y)
<preferred term2>	xx (yy.y)	xx (yy.y)	xx (yy.y)

System Organ Class and Preferred terms are based on MedDRA 25.1 dictionary.

Program: [program\\_name.sas](#), Produced on yyyy-mm-dd hh:mm (CET),  
 Snapshot date: yyyy-mm-dd, Draft/final

Page x of x

### 13.1.10 Layout T10

Study MMED007 - Deliverables: <Deliverables>

Table <Number of table>

<Title>

Analysis set: <analysis set>

Score: 

Visit

	MM-120 N=xx*	Placebo N=xx*
--	-----------------	------------------

Baseline

n	xx	xx
Mean	xx.x	xx.x
Standard deviation	xx.x	xx.x
Median	xx.x	xx.x
Q 1 , Q 3	xx.x, xx.x	xx.x, xx.x
Min, Max	xx.x, xx.x	xx.x, xx.x

Week <n>

n	xx	xx
Mean	xx.x	xx.x
Standard deviation	xx.x	xx.x
Median	xx.x	xx.x
Q 1 , Q 3	xx.x, xx.x	xx.x, xx.x
Min, Max	xx.x, xx.x	xx.x, xx.x

Change from Baseline to Week <n>

n	xx	xx
Mean	xx.x	xx.x
Standard deviation	xx.x	xx.x
Median	xx.x	xx.x
Q 1 , Q 3	xx.x, xx.x	xx.x, xx.x
Min, Max	xx.x, xx.x	xx.x, xx.x

Program: [program\\_name.sas](#), Produced on yyyy-mm-dd hh:mm (CET),

Snapshot date: yyyy-mm-dd, Draft/final

Page x of x

Note for programmer: Table will be presented by week: only subjects with both the baseline and specific time point assessment will be included.  refer to scores on 'Patient Reported Outcomes' eCRF page to be summarized in the table. In the table scores  should be reported as: A=Inattention/Memory Problems; B=Hyperactivity/Restlessness;

C=Impulsivity/Emotional Lability; D=Problems with Self-Concept; E=DSM-IV Inattentive Symptoms; F=DSM-IV Hyperactive-Impulsive Symptoms; G=DSM-IV ADHD Symptoms Total; H=ADHD Index.

Visit:

For scores ASRS and CAARS-L-SR: Week 2, Week 4, Week 6.

For scores AISRS and CGI-S: Week 2, Week 6.

### 13.1.11 Layout T11

Study MMED007 - Deliverables: <Deliverables>

Table <Number of table>

<Title>

Analysis set: <analysis set>

	MM-120 N=xx N (%)	Placebo N=xx N (%)
Compliance (%) categories		
100% (12/12)	xx (yy.y)	xx (yy.y)
91.7% (11/12)	xx (yy.y)	xx (yy.y)
83.3% (10/12)	xx (yy.y)	xx (yy.y)
etc.	xx (yy.y)	xx (yy.y)
Number of subjects with at least one Special Situation	xx (yy.y)	xx (yy.y)
Number of Special Situations	xx	xx
Special situation*:		
Medication error or incorrect drug administration	xx (yy.y)	xx (yy.y)
Overdose	xx (yy.y)	xx (yy.y)
Deliberate abuse	xx (yy.y)	xx (yy.y)
Deliberate misuse	xx (yy.y)	xx (yy.y)
Drug interaction	xx (yy.y)	xx (yy.y)
Occupational exposure	xx (yy.y)	xx (yy.y)

\*Percentages are computed on "Number of Special Situations"

Program: [program\\_name.sas](#), Produced on yyyy-mm-dd hh:mm (CET),

Snapshot date: yyyy-mm-dd, Draft/final

Page x of x

### 13.1.12 Layout T12

Study MMED007 - Deliverables: <Deliverables>

Table <Number of table>

<Title>

Analysis set: <analysis set>

	MM-120 N=xx	Placebo N=xx
Baseline		
n	xx	xx
Mean	xx.x	xx.x
Standard deviation	xx.x	xx.x
Median	xx.x	xx.x
Q 1 , Q 3	xx.x, xx.x	xx.x, xx.x
Min, Max	xx.x, xx.x	xx.x, xx.x
Week 2		
n	xx	xx
Mean	xx.x	xx.x
Standard deviation	xx.x	xx.x
Median	xx.x	xx.x
Q 1 , Q 3	xx.x, xx.x	xx.x, xx.x
Min, Max	xx.x, xx.x	xx.x, xx.x
Change from Baseline to Week 2		
n	xx	xx
Mean	xx.x	xx.x
Standard deviation	xx.x	xx.x
Median	xx.x	xx.x
Q 1 , Q 3	xx.x, xx.x	xx.x, xx.x
Min, Max	xx.x, xx.x	xx.x, xx.x
Absolute Change (from ANCOVA model)		
LS Mean	xx.x	xx.x
95% CL of LS Mean	xx.x, xx.x	xx.x, xx.x
TREATMENT EFFECT (MM-120 vs Placebo)		
p-value (based on ANCOVA model)	x.xxxx	

Program: [program\\_name.sas](#), Produced on yyyy-mm-dd hh:mm (CET),

Snapshot date: yyyy-mm-dd, Draft/final

Page x of x

### 13.1.13 Layout T13

Study MMED007 - Deliverables: <Deliverables>

Table <Number of table>

<Title>

Analysis set: <analysis set>

Visit

Category/Statistic	Baseline				
	0	1	2	...	6
<MM-120rm/Placebo > (N=xxx)					
Timepoint #1	0	## (##.#)	## (##.#)	## (##.#)	## (##.#)
	1	## (##.#)	## (##.#)	## (##.#)	## (##.#)
	...	## (##.#)	## (##.#)	## (##.#)	## (##.#)
	6	## (##.#)	## (##.#)	## (##.#)	## (##.#)
Missing	## (##.#)	## (##.#)	## (##.#)	## (##.#)	## (##.#)
Improved	## (##.#)				
95% CIs	(##.#, ##.#)				
Timepoint #2					
Timepoint #2	0	## (##.#)	## (##.#)	## (##.#)	## (##.#)
	1	## (##.#)	## (##.#)	## (##.#)	## (##.#)
	...	## (##.#)	## (##.#)	## (##.#)	## (##.#)
	6	## (##.#)	## (##.#)	## (##.#)	## (##.#)
Missing	## (##.#)	## (##.#)	## (##.#)	## (##.#)	## (##.#)
Improved	## (##.#)				
95% CIs	(##.#, ##.#)				
Etc...	## (##.#)	## (##.#)	## (##.#)	## (##.#)	## (##.#)

Percentages are based on N (number of patients in the analysis set)

Program: [program\\_name.sas](#), Produced on yyyy-mm-dd hh:mm (CET),

Snapshot date: yyyy-mm-dd, Draft/final

Page x of x

### 13.1.14 Layout T14

Study MMED007 - Deliverables: <Deliverables>

Table <Number of table>

<Title>

Analysis set: <analysis set>

	MM-120 N=xx N (%)	Placebo N=xx N (%)	All N=xx N (%)
Time since ADHD diagnosis, days			
n	xx	xx	xx
Mean	xx.x	xx.x	xx.x
Standard deviation	xx.x	xx.x	xx.x
Median	xx.x	xx.x	xx.x
Q1, Q3	xx.x, xx.x	xx.x, xx.x	xx.x, xx.x
Min, Max	xx.x, xx.x	xx.x, xx.x	xx.x, xx.x

Diagnostic criteria assessment according  
to DSMV

All criteria met	xx (yy.y)	xx (yy.y)	xx (yy.y)
Not all criteria met	xx (yy.y)	xx (yy.y)	xx (yy.y)
Complete CAARS-S-OR at screening			
Yes	xx (yy.y)	xx (yy.y)	xx (yy.y)
No	xx (yy.y)	xx (yy.y)	xx (yy.y)
If 'Yes':			
A Score			
n	xx	xx	xx
Mean	xx.x	xx.x	xx.x
Standard deviation	xx.x	xx.x	xx.x
Median	xx.x	xx.x	xx.x
Q1, Q3	xx.x, xx.x	xx.x, xx.x	xx.x, xx.x
Min, Max	xx.x, xx.x	xx.x, xx.x	xx.x, xx.x
B Score			
n	xx	xx	xx
Mean	xx.x	xx.x	xx.x
Standard deviation	xx.x	xx.x	xx.x
Median	xx.x	xx.x	xx.x
Q1, Q3	xx.x, xx.x	xx.x, xx.x	xx.x, xx.x
Min, Max	xx.x, xx.x	xx.x, xx.x	xx.x, xx.x
C Score			
n	xx	xx	xx
Mean	xx.x	xx.x	xx.x
Standard deviation	xx.x	xx.x	xx.x
Median	xx.x	xx.x	xx.x
Q1, Q3	xx.x, xx.x	xx.x, xx.x	xx.x, xx.x
Min, Max	xx.x, xx.x	xx.x, xx.x	xx.x, xx.x
D Score			
n	xx	xx	xx
Mean	xx.x	xx.x	xx.x
Standard deviation	xx.x	xx.x	xx.x
Median	xx.x	xx.x	xx.x
Q1, Q3	xx.x, xx.x	xx.x, xx.x	xx.x, xx.x
Min, Max	xx.x, xx.x	xx.x, xx.x	xx.x, xx.x
Current somatic disorder			
Yes	xx (yy.y)	xx (yy.y)	xx (yy.y)
No	xx (yy.y)	xx (yy.y)	xx (yy.y)
Previous hospitalization(s), previous disorders, (somatic and psychiatric), previous surgery(s)			
Yes	xx (yy.y)	xx (yy.y)	xx (yy.y)
No	xx (yy.y)	xx (yy.y)	xx (yy.y)
Family history (psychiatric and somatic)			
Yes	xx (yy.y)	xx (yy.y)	xx (yy.y)
No	xx (yy.y)	xx (yy.y)	xx (yy.y)
ADHD medication (prescription or non-prescription)			
Yes	xx (yy.y)	xx (yy.y)	xx (yy.y)
No	xx (yy.y)	xx (yy.y)	xx (yy.y)
Alcohol, caffeine, nicotine:			
Current Smoker			
Yes	xx (yy.y)	xx (yy.y)	xx (yy.y)
No	xx (yy.y)	xx (yy.y)	xx (yy.y)
Cigarettes per day			
n	xx	xx	xx
Mean	xx.x	xx.x	xx.x
Standard deviation	xx.x	xx.x	xx.x
Median	xx.x	xx.x	xx.x
Q1, Q3	xx.x, xx.x	xx.x, xx.x	xx.x, xx.x
Min, Max	xx.x, xx.x	xx.x, xx.x	xx.x, xx.x
Packs per year			
n	xx	xx	xx
Mean	xx.x	xx.x	xx.x
Standard deviation	xx.x	xx.x	xx.x
Median	xx.x	xx.x	xx.x
Q1, Q3	xx.x, xx.x	xx.x, xx.x	xx.x, xx.x
Min, Max	xx.x, xx.x	xx.x, xx.x	xx.x, xx.x
Coffee			
Yes	xx (yy.y)	xx (yy.y)	xx (yy.y)
No	xx (yy.y)	xx (yy.y)	xx (yy.y)
Coffee per day			
n	xx	xx	xx
Mean	xx.x	xx.x	xx.x
Standard deviation	xx.x	xx.x	xx.x
Median	xx.x	xx.x	xx.x
Q1, Q3	xx.x, xx.x	xx.x, xx.x	xx.x, xx.x
Min, Max	xx.x, xx.x	xx.x, xx.x	xx.x, xx.x

Alcohol (Beer, wine, liquor, ect.)			
Yes	xx (yy.y)	xx (yy.y)	xx (yy.y)
No	xx (yy.y)	xx (yy.y)	xx (yy.y)
Alcohol per week			
n	xx	xx	xx
Mean	xx.x	xx.x	xx.x
Standard deviation	xx.x	xx.x	xx.x
Median	xx.x	xx.x	xx.x
Q1, Q3	xx.x, xx.x	xx.x, xx.x	xx.x, xx.x
Min, Max	xx.x, xx.x	xx.x, xx.x	xx.x, xx.x
MDMA/Ecstasy			
Yes	xx (yy.y)	xx (yy.y)	xx (yy.y)
No	xx (yy.y)	xx (yy.y)	xx (yy.y)
Sedative, Narcotic (Benzos, Ketamine, Laughing gas (nitrous oxide))			
Yes	xx (yy.y)	xx (yy.y)	xx (yy.y)
No	xx (yy.y)	xx (yy.y)	xx (yy.y)
Hallucinogenic (LSD, Mescaline, Psilocybin)			
Yes	xx (yy.y)	xx (yy.y)	xx (yy.y)
No	xx (yy.y)	xx (yy.y)	xx (yy.y)
Stimulants (Amphetamine, Cocaine, Methylphenidate (recreationally))			
Yes	xx (yy.y)	xx (yy.y)	xx (yy.y)
No	xx (yy.y)	xx (yy.y)	xx (yy.y)
Opioids (Morphine, Diacetylmorphin, Codeine, Methadone)			
Yes	xx (yy.y)	xx (yy.y)	xx (yy.y)
No	xx (yy.y)	xx (yy.y)	xx (yy.y)
Cannabis, Marijuana, CBD			
Yes	xx (yy.y)	xx (yy.y)	xx (yy.y)
No	xx (yy.y)	xx (yy.y)	xx (yy.y)
Others: (GHB, PCP, DXM, Spice)			
Yes	xx (yy.y)	xx (yy.y)	xx (yy.y)
No	xx (yy.y)	xx (yy.y)	xx (yy.y)

Program: `program_name.sas`, Produced on yyyy-mm-dd hh:mm (CET),

Snapshot date: yyyy-mm-dd, Draft/final

Page x of x

Note for Programmer: CAARS-S-OR scores should be reported in the table as: A-Score=DSM-IV Inattentive Symptoms; B-Score=DSM-IV Hyperactive/Impulsive Symptoms; C-Score=DSM-IV ADHD Symptoms Total; D-Score=ADHD Index.

### 13.1.15 Layout T15

Study MMED007 - Deliverables: <Deliverables>

Table <Number of table>

<Title>

Analysis set: <analysis set>

Visit

	MM-120 N=xx N (%)	Placebo N=xx N (%)	All N=xx N (%)
Test performed			
Yes	xx (yy.y)	xx (yy.y)	xx (yy.y)
No	xx (yy.y)	xx (yy.y)	xx (yy.y)
Missing	xx (yy.y)	xx (yy.y)	xx (yy.y)
Stop signal task			
Done	xx (yy.y)	xx (yy.y)	xx (yy.y)
Not done	xx (yy.y)	xx (yy.y)	xx (yy.y)
Missing	xx (yy.y)	xx (yy.y)	xx (yy.y)
Discounting task			
Done	xx (yy.y)	xx (yy.y)	xx (yy.y)
Not done	xx (yy.y)	xx (yy.y)	xx (yy.y)
missing	xx (yy.y)	xx (yy.y)	xx (yy.y)
Psychomotor Vigilance Task			
Done	xx (yy.y)	xx (yy.y)	xx (yy.y)
Not done	xx (yy.y)	xx (yy.y)	xx (yy.y)
Missing	xx (yy.y)	xx (yy.y)	xx (yy.y)

Time Production Task		xx (yy.y)	xx (yy.y)	xx (yy.y)
Done		xx (yy.y)	xx (yy.y)	xx (yy.y)
Not done		xx (yy.y)	xx (yy.y)	xx (yy.y)
Missing		xx (yy.y)	xx (yy.y)	xx (yy.y)
Time Reproduction Task		xx (yy.y)	xx (yy.y)	xx (yy.y)
Done		xx (yy.y)	xx (yy.y)	xx (yy.y)
Not done		xx (yy.y)	xx (yy.y)	xx (yy.y)
Missing		xx (yy.y)	xx (yy.y)	xx (yy.y)

Program: `program_name.sas`, Produced on yyyy-mm-dd hh:mm (CET),  
 Snapshot date: yyyy-mm-dd, Draft/final

Page x of x

Note for Programmer: Visit = Baseline, Week 6. Please report No/Note done only if such data is available in the data. If it is not available, report Yes/Done values and missing for subjects where no data is available in the data set. All percentages should be calculated on the N.

### 13.1.16 Layout T16

Study MMED007 - Deliverables: <Deliverables>

Table <Number of table>

<Title>

Analysis set: <analysis set>

Severe ADHD (AISRS score at baseline  $\geq$  38) | Moderate ADHD (AISRS score at baseline  $<$  38)

Visit Treatment group	n	LS Mean	SE	95% CL	Difference to placebo				p-value*
					LSMean	SE	95% CL		
Change from Baseline to Week 6									
MM-120	xx	xx.x	xx.x	[xx.x, xx.x]	xx.x	xx.x	[xx.x, xx.x]	0.xxx	
Placebo	xx	xx.x	xx.x	[xx.x, xx.x]	-	-	-	-	

\*p-value is one-sided

\*\*MMRM=Mixed Model for Repeated Measures

Program: `program_name.sas`, Produced on yyyy-mm-dd hh:mm (CET),

Snapshot date: yyyy-mm-dd, Draft/final

Page x of x

Note for programmer:

-for "MMRMAISRS" dependent variable is AISRS Score (analysis performed on FAS);  
 -for "MMRMAR" dependent variable is AISRS Score, with MAR assumption (analysis performed on FAS); add Footnote: \*\*\* MAR= Missing At Random.  
 -for "MMRMNAR" dependent variable is AISRS Score, with MNAR assumption (analysis performed on FAS); add Footnote: \*\*\* MNAR= Missing Not At Random.  
 -for "MMRMCP" dependent variable is AISRS Score, completed cases (analysis performed on FAS)  
 -for "MMRMAISRS" dependent variable is AISRS Score (analysis performed on PPS)

Please use subgroups 'Severe ADHD (AISRS score at baseline  $\geq$  38) | Moderate ADHD (AISRS score at baseline  $<$  38)' in the sensitivity analysis of the MMRMAISRSSEV

### 13.1.17 Layout T17

Study MMED007 - Deliverables: <Deliverables>

Table <Number of table>

<Title>

Analysis set: <analysis set>

Number of Subjects considered in the model		xx	xx		
MM-120					
Placebo					
Shift values	0	LSMean	SE	95% CL	p-value
1	xx.x	xx.x	xx.x	[xx.x, xx.x]	0.xxx
2	xx.x	xx.x	xx.x	[xx.x, xx.x]	0.xxx
3	xx.x	xx.x	xx.x	[xx.x, xx.x]	0.xxx
...	xx.x	xx.x	xx.x	[xx.x, xx.x]	0.xxx

Note 1: Analysis is based on a Tipping Point analysis for primary endpoint

Note 2: Tipping point is performed until the MMRM model results to be not significant (p-value  $\geq$  0.05).

Program: `program_name.sas`, Produced on yyyy-mm-dd hh:mm (CET),

Snapshot date: yyyy-mm-dd, Draft/final

Page x of x

Note for programmer:

The Tipping point analysis will be performed only in case the main analysis of the primary endpoint (MMRMAISRS) resulted significant, p-value < 0.05.

The vector of shift values will include the values: ( $\delta = 0, 1, 2, 3, \dots$ ) until the first value when MMRM model results to be not significant (p-value  $\geq 0.05$ ).

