13.6.4. Sample size determination

Randomizing 26 subjects per arm, if the true efficacy of MM-120 reaches a standardized mean improvement over placebo of 0.60, the null hypothesis that active is not better than placebo will be rejected with a one-sided p-value < 0.10 with 80% power.

The minimum estimated standardized effect size resulting in a p-value < 0.10 is 0.38 while an estimated standardized effect size < 0.56 will result in a one-sided p-value < 0.025.

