### 10.7.1 Statistical model and hypotheses

The null hypothesis is that active MM-120 is not better than placebo; this will be rejected with a one-sided p-value < 0.10 with 80% power if the true efficacy of MM-120 reaches a standardized mean improvement over placebo of 0.60.

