#### ***10.7.3.1 Tipping point sensitivity analysis***

For the imputation of missing data of AISRS, MI will be implemented assuming the MAR and imputing all missing data including missing data occurred/imputed after IEs as described in policy strategies 1 and 2. A delta-adjusted imputation method will be used applying progressive stress test to the MAR assumption of the main analysis. That is, a tipping-point analysis will be performed to see how severe departures from the MAR assumption should be to overturn the conclusions of the main analysis. It is assumed that study subjects from the MM-120 group with missing values would have, on average, their observed efficacy score worsened by some amount (delta) compared

with the efficacy score observed in study subjects of the same MM-120 group remaining in the study. A series of analysis models defined above with progressively increasing deltas ( $\delta = 0, 1, 2, 3, \dots$ ; from less conservative to more conservative, where a delta of zero,  $\delta(0)$ , corresponds to the reference) will be run until the model results to be not significant ( $p\text{-value} \geq 0.05$ ). The delta adjustment will only be applied to the multiple-imputed values (based on the MAR assumption) of the subjects in the MM-120 group. Same linear mixed effects model defined for the main analysis will be used.

The Tipping point analysis will be performed only in case the main analysis of the primary endpoint resulted significant.

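### The tipping-point analysis is started and stopped at p = 0.05, although the primary test succeeds at one-sided p < 0.10

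*SAP*

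**What the plan says.** **Primary test.** SAP 10.7.1 says of the null hypothesis that "this will be rejected with a one-sided p-value < 0.10 with 80% power" when the true standardized improvement is 0.60. Protocol 13.6.4 sets the same level. The reported primary p-value is one-sided: SAP 10.7.2.2 asks for one, and Layout T16, the shell for the primary table (MMRMAISRS), carries the footnote "p-value is one-sided".

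**Purpose of the tipping-point analysis.** SAP 10.7.3.1 says it is run to see "how severe departures from the MAR assumption should be to overturn the conclusions of the main analysis".

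**Stopping rule.** Delta is added to the imputed MM-120 values in steps of 0, 1, 2, 3 and so on. The models "will be run until the model results to be not significant", which 10.7.3.1 defines as p of 0.05 or more. Layout T17 repeats this in Note 2 ("Tipping point is performed until the MMRM model results to be not significant", again at 0.05) and in a programmer note.

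**Starting rule.** SAP 10.7.3.1 gives no level: "The Tipping point analysis will be performed only in case the main analysis of the primary endpoint resulted significant". Another T17 programmer note supplies one: "The Tipping point analysis will be performed only in case the main analysis of the primary endpoint (MMRMAISRS) resulted significant, p-value < 0.05".

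Neither place says whether 0.05 is one-sided or two-sided. SAP 12.4.2 lists the tipping-point table as a key deliverable.

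**The concern.** The conclusion of the main analysis is a rejection at one-sided 0.10, so it is overturned when the one-sided p-value reaches 0.10. A rule that stops at 0.05 answers a different question. Two things follow.

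- **Trigger.** A primary one-sided p between 0.05 and 0.10 is a declared success, but T17 then omits the analysis. These are the weakest positive results, for which sensitivity to missing data matters most.
- **Stop.** When the analysis runs, it generally ends at a smaller delta than the one that reverses the conclusion. The table would then understate how robust the result is by the trial's own criterion.

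The text of 10.7.3.1 and the T17 shell also differ on the trigger, so the result depends on which one the programmer follows.

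**Working it through.** **Inputs.** 26 per arm, one-sided 0.10, 80% power and a design effect of 0.60 SD (Protocol 13.6.4, SAP 10.7.1); the 0.05 start and stop (SAP 10.7.3.1, T17). The model is an unadjusted two-sample t-test with 50 df. The planned analysis is a covariate-adjusted MMRM with multiple imputation, so the figures are approximate.

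**1. Reproduce the plan's power.** The standard error of the standardized difference is √(2/26) = 0.2774. At a true effect of 0.60 and one-sided 0.10, power is 0.806 (noncentral t) or 0.811 (normal approximation). The stated 80% is reproduced, which confirms one-sided 0.10 as the working criterion.

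**2. Observed effect needed** (critical t × 0.2774).

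- One-sided 0.10: 1.2987 × 0.2774 = 0.360 SD.
- One-sided 0.05: 1.6759 × 0.2774 = 0.465 SD.
- Two-sided 0.05 (one-sided 0.025): 0.557 SD.

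With 0.05 read one-sided, effects from 0.360 to 0.465 SD are successes with no tipping-point analysis under T17. Protocol 13.6.4 states: "The minimum estimated standardized effect size resulting in a p-value < 0.10 is 0.38". That minimum does not reproduce at 26 per arm (0.360 here), but an observed 0.38 gives t = 0.38/0.2774 = 1.370 and one-sided p = 0.088. The protocol's own minimum success therefore lies in the gap.

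**3. How often this happens** (noncentral t, 0.05 one-sided).

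| True effect | Power at 0.10 | Power at 0.05 | Difference | Share of positive trials |
|---|---|---|---|---|
| 0.40 | 0.559 | 0.412 | 0.147 | 26% |
| 0.60 | 0.806 | 0.688 | 0.119 | 15% |
| 0.80 | 0.943 | 0.885 | 0.058 | 6% |

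Read two-sided, the power to trigger at 0.60 is 0.564. The gap is then 0.806 − 0.564 = 0.242, or 30% of positive trials.

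**4. Size of the reported delta.** Let d be the standardized effect at delta zero. In 10.7.3.1 this is the analysis with all missing data imputed under missing at random. If a share m of the MM-120 arm is imputed, adding delta lowers the treatment difference by m × delta. With the standard error held fixed, the delta that reaches a given level is SD × (d − cut-off)/m. SD and m cancel in the ratio:

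delta(0.05)/delta(0.10) = (d − 0.465)/(d − 0.360)

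- d = 0.50: 0.035/0.140 = 0.25
- d = 0.60: 0.135/0.240 = 0.56
- d = 0.80: 0.335/0.440 = 0.76

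Allowing for the variance that the shift adds within the arm, with 3, 5 or 8 of 26 missing (an assumed range), gives 0.26–0.27, 0.57–0.58 and 0.76. Read two-sided, the ratio at d = 0.60 is (0.60 − 0.557)/(0.60 − 0.360) = 0.18.

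**5. In AISRS points.** The documents give neither an SD nor a missing share. Assuming SD 10, d = 0.60 and 15% imputed, the 0.10 criterion is crossed at about 10 × 0.240/0.15 = 16 points. The one-sided 0.05 rule is crossed at about 9 points (first integer step 10), and the two-sided rule at about 2.9 (step 3). Over SD 8–12, d 0.5–0.7 and 10–30% imputed, the one-sided 0.05 rule gives about 25% to 69% of the 0.10 delta.

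**The case against.** **The 0.05 has a source.** SAP 10.1 sets 0.05 as the general level, with two-tailed 95% intervals. But that default yields wherever another level is specified, and 10.7.1 specifies one for this hypothesis. Appendix D lists no departure for the tipping-point analysis.

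**Sidedness is unsettled.** T17 has no one-sided footnote and prints 95% limits, so a two-sided reading is possible. This stands. The trigger refers to the primary p-value, which is reported one-sided, and that supports the milder reading. The two-sided reading only makes the gap larger.

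**The trigger level rests on one shell note.** Section 10.7.3.1 alone could be read together with 10.7.1 as one-sided 0.10. However, the same section treats p of 0.05 or more as not significant, which works against that reading.

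**The consequence is limited.** This largely stands. Stopping early understates robustness and cannot exaggerate it, and on an integer grid the two rules may occasionally stop at the same step. The main analysis already imputes from placebo after prohibited medication or discontinuation. The copy-reference, complete-case, per-protocol and severity analyses run regardless. But none of them measures how large a departure reverses the result, which is the purpose of this analysis.

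**The protocol sets no condition at all.** Protocol 13.6.2 commits to a worse-than-MAR penalty analysis without requiring significance. That counts further against the 0.05 trigger.

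**Conclusion.** The concern holds. Followed as written, T17 gives no tipping-point analysis for some successful trials, and T17 and 10.7.3.1 together give a delta that is generally too small for the rest. At the design effect, about 12% of all trials (15% of positive ones) would be positive without the analysis if 0.05 is one-sided, and about 24% (30% of positive ones) if it is two-sided. When it runs, the one-sided rule reports about a quarter to three quarters of the relevant delta for effects of 0.50 to 0.80 SD at delta zero. The sizes rest on the unadjusted t approximation with 26 per arm, and the point values on an assumed SD and missing share. The existence of the mismatch depends on none of these. The primary test is unchanged. This should be fixed, but it does not threaten the trial's main inference.

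**What to change.** In SAP 10.7.3.1, state that the analysis runs when the primary one-sided p-value is below 0.10 and that delta is raised until the one-sided p-value is 0.10 or more. Make the same change in Layout T17, in Note 2 and both programmer notes, and add the one-sided footnote already used in T16. The delta at which p crosses 0.05 can be kept as an extra row, with its sidedness stated. The cost is wording in one SAP section and one table shell, plus a few more delta runs.
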